KØBENHAVNS UNIVERSITET - TANDLÆGESKOLEN

Forsøgsprotokol Jf. GCP-enhedens protokolvejledning

(The main research protocol is developed based on the guidelines for Good Clinical Practice (GCP))

1. Title:

DIMOH: New **Di**gital **M**ethods for **M**onitoring **O**ral **H**ealth. An i*n vivo* assessment. Odontologisk Institut - Tandlægeskolen Det Sundhedsvidenskabelige Fakultet Københavns Universitet [name]

2. Objectives

The objectives of this study are *i*) to monitor the oral health of young people over a period of 12 months and *ii*) to assess the ability of a new intraoral scanner combining fluorescence (from emitted blue light) with 3D imaging to detect and monitor changes in the dental hard tissues *in vivo*.

a. Hypotheses

The working hypotheses of this study are:

- 1. The monitoring of oral health will benefit from using a new intraoral scanner combining fluorescence with 3D imaging.
- 2. The new intraoral scanner combining fluorescence with 3D imaging will aid dentists to identify changes in the dental hard tissues at earlier stages than the traditional diagnostic methods (*i.e.* visual-radiographic methods).

b. Background

Literature Review and Research Question

Currently, monitoring oral health relies mainly on the visual examination of the oral tissues by the dental professional, aided electively by radiographic or photographic images (1, 2). In the context of oral health, monitoring involves detecting changes, sometimes rather subtle, in the soft or hard oral tissues; such changes are associated with the development of oral diseases or ageing (3, 2). Through the course of their lives, people will experience changes in the level of gingiva, increments on the teeth surface due to calcification of biofilm, loss of mineral tissues due to caries or tooth wear, wear of restorative materials, or modification in the in the position or color of the teeth. The slow rate of change involved in some of these situations makes it extremely difficult for the human eye alone to identify them. It is even more challenging to accurately register and recall the original situation on the patient's follow-up visits. Clinical photographs are therefore used to aid the monitoring (4, 2); however, it is difficult to obtain comparable photographs from different points in time and the subjectivity involved in the process cannot be avoided.

Different criteria are used in clinical practice to register and monitor changes in the oral tissues, according to the specific condition under investigation. While identifying significant changes is an easy task, the challenge lies particularly in identifying early, incremental changes. Regarding the detection of caries lesions, a number of initial lesions typically remain unnoticed when visual examination alone is used (5); or even when radiographs are employed, as the latter are not sensitive to early demineralization in enamel (6). Concerning tooth wear (*i.e.* erosion, abrasion, attrition), as the gradual mineral loss occurs progressively and irreversibly, it is usually only noticed when a significant amount of hard dental tissue is already lost (2). Additionally, minor changes on the gingival level, *e.g.* resulting from improper oral hygiene habits or yet an early inflammation of the periodontal tissues, may pass unnoticed to the dental personnel.

A promising clinical solution to overcome the challenges involved in the detection of early changes and monitoring of oral tissues is the use of 3D intraoral scans (7, 8). 3D scans obtained from gypsum models (*ex vivo*) have previously been used to identify changes of tooth position (9, 10), gingiva volume (11, 12), loss of mineral tissues (13) or wear of restorative materials (14). Although gypsum models offer information about volumetric changes (*e.g.* tooth

substance loss, movement of teeth, gingival level, stagnation of biofilm), the color information is lost. However, color is a valuable parameter for the previously mentioned clinical criteria as it is one of the parameters used to identify diseases (*e.g.* caries, gingivitis) or other oral conditions (*e.g.* tooth discoloration due to ageing, tooth whitening or discoloration of dental materials) (15, 2). Hence, obtaining 3D scans directly from the patients (*in vivo*) using intraoral scanners is desired, as these scans contain color information of the natural tissues. Additionally, by comparing 3D scans obtained from the same patients at different points in time, a less subjective and more reliable comparison of data is expected: the 3D scans can be overlapped and analyzed using specific software (9, 7, 16). Therefore, it is hypothesized that 3D intraoral scans can be used for more consistent monitoring of oral health in relation to clinical photographs or clinical records.

The current 3D intraoral scanners capture the color of the oral tissues by emitting visible white light. A recently developed 3D intraoral scanner manufactured and CE marked by 3Shape A/S. Denmark, is also able to emit visible blue light (405 nm wavelength) (17) that allows capturing fluorescence from the oral tissues. Fluorescence is one of the most promising technologies for accurate detection of the early stages of enamel demineralization (18, 19, 20), but is currently available only in 1D or 2D devices. The main limitation of the existing devices featuring fluorescence, as already mentioned, is the challenge in comparing single images obtained at different points in time, which is at large influenced by imaging artifacts and noise. Imprecision in the comparison of these images compromises the ability to accurately monitor progressive demineralization of the dental hard tissues. To the best of our knowledge, there is no intraoral scanner reported in the scientific literature that combines fluorescence with 3D imaging. Thus, we hypothesize that this new intraoral scanner will benefit the monitoring of dental hard tissues and will aid dentists to identify early changes in tissue mineralization. With this method it is only possible to examine the tooth surfaces that are visible and directly exposed into the mouth (i.e. the smooth free surfaces and the occlusal fissures); the areas between the teeth (i.e. the approximal surfaces) cannot be visualized and therefore cannot be examined using the scanner.

3. Methods

Study execution

The participants will be monitored for a period of 1 year. The study will last approximately 2 years in total, with the baseline examination taking place in the beginning of 2019 and the last examination in the Spring – Winter 2020. Detailed plan of the study is shown in Table 1.

Information about the project

Potential participants will find contact information of the responsible researcher on diverse project announcements. By contacting the responsible researcher, the potential participants accompanied by their parents/guardians (in case of underage candidates) will be able to book time for an information meeting regarding the clinical oral examination and will receive detailed written information material about the study. Appropriate language will be used to make sure that the information is clearly understood by all potential participants. The potential participants and their parents/guardians will be asked to read the written information before the in-person information meeting.

The in-person information meeting will take place in a room where no disturbances can occur. All underage candidates should be accompanied by their parents/guardians. The responsible

researcher will inform the potential participants about the study and the clinical procedures. The responsible researcher is a dentist with experience in communicating with young patients and has finalized pedagogical training. Therefore, she fulfills the prerequisites to be the responsible person to inform the young participants.

After attending the information meeting and they (for adults) or the parents/guardians (for underage) receiving a copy of the inform/parental consent, 24 - 48 hours will be allowed to decide about participation. Furthermore, they will all be informed about the voluntary nature of participation in the study and the freedom to withdraw – at any time – their participation. All potential participants will receive the documents "Før du beslutter dig" which includes the "Forsøgspersoners rettigheder i et sundhedsvidenskabeligt forskningsprojekt", which they are encouraged to read thoroughly. Copies in Danish and English will be provided for the Danish and Greek participants respectively.

Participants who decide to join the study will be asked to fill out a 4-day diet history, from Friday through Monday (Appendix 1). There the participants should register everything that they eat and drink, excluding water. Furthermore, they will be asked to fill out a questionnaire regarding their oral hygiene habits (Appendix 2). Both forms will be provided at the in-person information meeting, together with the copy of the inform/parental consent. All forms should be delivered on the second appointment (baseline examination).

Clinical and radiographic examination

A second appointment will be scheduled to conduct the oral health examination, including intraoral scanning and 2 bitewing radiographs (BW). The responsible researcher will request the participants to provide any recently available BW, in case these are not older than 6 months. No study-related examination will be conducted before the signed parental consent form has been obtained by the responsible researcher. The participants will not be offered any treatment other than routine professional tooth cleaning, which is important for a thorough visual examination and scanning of the teeth. In case any oral disease is detected, the participants will be referred to their dentist for treatment.

If no radiographs are available from the past six months, BW of the upper and lower posterior teeth on both sides will be taken. Since radiographs are part of the participants' annual dental check-up, these will be made available to the participants' dentist. Additionally, an oral examination will be conducted, and the condition of teeth, gums and fillings will be registered. The approximal plaque accumulation will be registered by employing the approximal plaque index (21). Thereafter, the teeth will be professionally cleaned, and the presence of caries lesions will be registered based on the visual and radiographic assessments. Caries lesions will be characterized as active or inactive and classified according to the ICDAS criteria into 7 stages (22). Furthermore, the presence of other visible defects on the oral hard tissues (*i.e.* erosive – abrasive lesions) will be registered using appropriate criteria (*i.e.* BEWE index for erosive tooth wear) (2, 23).

Subsequently, both the upper and lower jaw of the participant will be scanned using the intraoral scanner (Trios 4, 3Shape Trios A/S, Denmark). Scans will be obtained using visible white and blue light (wavelength 415 nm).

At the end of the session, the participants will be classified into different risk groups (low, moderate, high) according to the clinical findings and the information collected from the diet

history and the oral hygiene habits questionnaire (Appendix 1, 2). According to this classification, the responsible researcher will set the follow-up intervals for each participant (3-12 months). All patients will be monitored for 1 year.

The same clinical procedures will be followed on the follow-up examinations (3 or 6 months) as well as on the final examination (1-year follow-up). The diet history, the oral hygiene habits questionnaire and the BW radiographs will be repeated only on the final examination (Table. 1).

4. Statistics

Paired T-test will be conducted to identify differences between the clinical scores at the baseline and the subsequent follow-ups for the different conditions investigated (*i.e.* caries score, erosion score) (24).

Exploratory analysis of the data extracted from the 3D scans will be conducted and compared to the clinical scores. Pearson correlation coefficients between the clinical scores and scores obtained from the 3D scans will be calculated. Paired t-test will be conducted to compare the number of lesions per patient (*i.e.* caries, tooth wear) that will be detected with the 2 different methods (scanning and clinical-radiographic examination).

All statistical analysis will be conducted using a 95% level of confidence.

Information regarding the sample size calculation using power analysis is provided on the following paragraph (§5. Research subjects - Sample size calculation)

5. Research subjects

The participants in this research project will be adolescents (12-16 years old) and young adults (18-19 years old) in Denmark and in Greece respectively.

As previously mentioned, this project will assess the ability of the intraoral scanner combining fluorescence to detect and monitor initial changes in the dental hard tissues, with special focus on caries: the most prevalent oral disease. The most important benefit expected by using the fluorescence method is the detection of initial lesions on dental surfaces directly exposed to the mouth. Fissure lesions in permanent posterior teeth usually appear in the long-lasting period of tooth eruption, *i.e.* from when the tooth first appears in the mouth until it contacts with the opposite dentition (28). Eruption of the first permanent molar starts around the ages of 6-8 years, the second molar at 12-14 years (28) and the third molar at 17-18 years. During the eruption period, the posterior teeth are at a higher risk for developing fissure caries. For the second permanent molars, this period can last up to 27 months form the first appearance in the mouth (~12 years old) (29) though for the third molars this period is usually longer.

The initial state of the caries lesion is short-lived before progression of the disease. In older patients, caries lesions in fissures are either found at more advanced stages or they have already been treated by the dentist (*i.e.* sealed, filled or extracted as in the case of third molars) (28). Although initial caries lesions can be found in older patients, such initial lesions are located on the surfaces between the teeth, which are not visible to the intraoral scanner and therefore cannot be detected using this method.

For these reasons, the age group is set from 12 to 19 years. It is necessary to conduct the study on this group of young people, as the study is expected to benefit them directly. The same benefits are not expected if the study is conducted in older adults.

The early diagnosis of initial lesions in the young participants is more beneficial as it will allow the implementation of preventive measures to stop the progression of the disease. This will decrease the complexity of the treatments needed in the target group, as the initial lesions can be treated with minimal or non-invasive approaches. Thus, the economic burden for the state regarding treatment expenses of the adolescents and the individual costs related to future dental treatment will be reduced.

Inclusion criteria:

- Young people (12-19 years old) without chronic diseases.

Exclusion criteria:

- Participants in need of complex dental treatment (*e.g.* extensive restorative work, extractions, prosthetic treatment).
- Participants using partial/complete removable dentures or other appliances (*i.e.* orthodontic devices).

Sample size calculation

Caries data was used in order to calculate the desirable sample size for the current study, as that is the most prevalent oral disease in young patients and is widely investigated in epidemiological studies (1). Therefore, data regarding initial caries lesions was used for the sample size calculation, assuming that the new method will aid dentists to detect significantly more initial caries lesions compared to traditional methods.

For the sample size calculation, data collected by the Central Odontology Register of the Danish National Board of Health (Sundhedsstyrelsens Centrale Odontologiske Register SCOR) during the year 2017 from municipal dental clinics at 98 different municipalities in Denmark was used. According to the data, an average of 3.08 initial lesions, with a standard deviation of 1.23 were identified on 15-year old patients at the different municipalities. In this study, the desirable power was set on 90%, the level of significance on 5% and the effect size on 30% (1 lesion). By applying these parameters, the sample size was calculated to be 64 adolescents. Nevertheless, as a 10% drop-out is expected for this type of study, the final number of participants to be included in the study should be 70.

6. Risks, side effects and shortcomings in short and long term

Risks

This study will be conducted on healthy persons, on whom the procedures followed in this study are assumed to have a negligible risk.

No risk is related to the clinical visual examination.

Regarding the 3D intraoral scanning procedure, if the scan quality is poor and thus the scan is not useful for the research objectives, the scanning procedure should be repeated. This is of no risk for the patient but represents the inconvenience of a delay of the dental visit.

For the scanning using blue light (wavelength 415nm) possible risks exist. For the participant, light irritation of the mucosa and lips may result from a local, acute overexposure to the strong blue light. This irritation, though, is mild and temporary. For the operator, possible harm to the eyes, especially on the lenses and the retinal tissues, may be caused by long-term cumulative exposure to blue light. These risks are not particular for this specific intraoral device but are

common to any dental equipment that uses blue light. Having these risks in mind, the equipment will be used properly and with care: the exposure time will be limited to 15 seconds per tooth and direct exposure to mucous membranes will be avoided. The equipment will be started only after it has been inserted into the patient's mouth. The operator will avoid looking directly into the mouth and instead will look on the computer screen during the scanning procedure. Eye-protection goggles filtering light under 500 nm are suggested to be used by the operator.

According to the Classification for Medical Devices in Europe, the mentioned 3D scanner is a Class 1 device and therefore is considered of low risk. All in all, minimal risks are at stake for the participants and the operator under proper use of the equipment. Any safety issues will be reported to the manufacturers, the VEK and the Patient Safety Board.

Side-effects

There is no side effect from the clinical examination or the scanning.

The radiation dose used for the acquisition of the dental radiographs varies between 1-10 μ Sv, depending on the technique used, and is equivalent to the average background radiation dose for 2-20 hours (the natural background radiation in Denmark is 3 mSv per year) (25). This project is classified as Category 1 according to the guidelines from the International Commission of Radiation Protection (ICRP) and the European Commission (26, 27). The overall stochastic effect from the exposure of the participants to ionizing radiation is estimated to be 1 in 1 million or smaller and the risk is thus considered insignificant.

Shortcomings:

All the procedures followed in the study (scheduling, radiographs, dental check-up, scanning) are time consuming and may inconvenience the participants.

7. Biological material

No biological material will be obtained from the participants or from another existing biobank.

8. Information from the participants' medical journal

No information will be retrieved from the participants' medical journal. The required information for the present study will be extracted from the participants during the clinical examination and scanning. All information will be registered on the digital dental journal used internally at the Dental Schools of the University of Copenhagen and the National and Kapodistrian University of Athens (for the Danish and Greek participants respectively. External, unauthorized people do not have access to this database.

Recent BW radiographs (no older than 6 months) will be retrieved from the participants' dental journal only after the participants' consent.

9. Data handling

The data will include the condition of oral health (plaque, caries, tooth wear etc.) gathered from the visual and radiographic assessments, as well as from the 3D scans. All data and sensitive personal information obtained from the participants will be treated and stored in compliance with the EU General Data Protection Regulation (GDPR) and following good research ethics.

10. Participant Recruitment

The study will be advertised at local schools and at the Dental Schools of the University of Copenhagen and the National and Kapodistrian University of Athens (on announcement boards and/or on the schools' webpages) and eventually giving presentations about the study by the responsible researcher. Further information regarding the informed consent and the in-person information meetings with the participants are provided on paragraph §3. Methods – Information about the project.

11. Research Ethics

The physical and mental integrity of the participants, as well as their privacy, will be respected. The good clinical practice (GCP) guidelines and EU General Data Protection Regulation (GDPR) will be followed.

Benefits of the Study

The risks, shortcomings and side effects (see above) are surpassed by the benefit of early diagnosis of oral diseases. The early diagnosis benefits the participants because oral problems can be treated more easily before they develop into more severe problems. The early detection of oral diseases is crucial, as often the problems can be treated non-invasively and different preventive strategies can be implemented to stop disease progression.

Additionally, the 3D intraoral scanner has the potential to aid dentists identifying changes in the oral tissues at earlier stages than with the visual – radiographic examinations. If this concretizes, the use of this equipment may potentially reduce the need for ionizing radiation for detecting oral problems and monitoring oral health, something that would be of significant benefit to all patients.

12. Participant compensation

This study is carried out on healthy persons under the direct responsibility of the dental school – University of Copenhagen. Thus, possible injuries to participants will be covered by the Danish "Patienterstatningen".

Hovedprotokol Version 3 Date: 8.1.2019

Table 1. Study Plan

Information meeting (~20 min)	Baseline examination January – September 2019 (~60 min)	3-month / 6-month follow-up examination (only for moderate/high risk groups) July 2019-March 2020 (~45 min)	1-year follow-up Final examination April – September 2020 (~60 min)	Study Termination September – December 2020
 Oral information about the clinical examination Distribution: Inform consent agreement Diet history registration form Questionnaire about oral hygiene habits 	 Registration of diet history and oral hygiene habits Clinical examination (registration of plaque, caries and other findings) Teeth cleaning Radiographic examination Scanning Participant risk assessment – Set follow-up intervals Data selection and management 	 Clinical examination (registration of plaque, caries and other findings) Teeth cleaning Scanning Data selection and management 	 Registration of diet history and oral hygiene habits Clinical examination (registration of plaque, caries and other findings) Teeth cleaning Radiographic examination Scanning Data selection and management 	 Data management Statistical analysis Publication

References

- 6) Mejàre I, Axelsson S, Dahlén G, Espelid I, Norlund A, Svensson Å, Tranæus S, Twetman S. The Swedish Council on Technology Assessment in Health Care. Karies diagnostik,
- riskbedömning och icke-invasiv behandling. En systematisk litteraturöversikt. 2007; 403p.

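### Reused baseline bitewings can be up to 6 months old, so lesions seen only on film that formed before baseline can count as 1-year caries change

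*Combined protocol and SAP*

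**What the plan says.** Section 3 (Clinical and radiographic examination) has the researcher "request the participants to provide any recently available BW, in case these are not older than 6 months". New films depend on that request: "If no radiographs are available from the past six months, BW of the upper and lower posterior teeth on both sides will be taken". Section 8 agrees: "Recent BW radiographs (no older than 6 months) will be retrieved from the participants' dental journal only after the participants' consent".

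The rest of the baseline assessment happens at one appointment. After cleaning, "the presence of caries lesions will be registered based on the visual and radiographic assessments". Then, "Subsequently, both the upper and lower jaw of the participant will be scanned using the intraoral scanner". Interim follow-ups repeat the clinical procedures, but "the BW radiographs will be repeated only on the final examination".

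Section 4 plans two paired t-tests that use these data. One compares clinical scores, including the caries score, between baseline and follow-up. The other compares lesions per patient between the scan and the clinical-radiographic examination. Neither mentions film date, film age or the mix of reused and new films.

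**The concern.** A reused film describes an earlier mouth than the one examined and scanned at baseline. The protocol gives reason to think a few months can matter in caries: section 5 says that "The initial state of the caries lesion is short-lived before progression of the disease", although the surrounding text is mainly about fissures.

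The main consequence is for the change analysis. Suppose a lesion visible only on a bitewing forms after the old film but before the baseline visit. It is absent from the baseline score and present in the 1-year score, so it counts as change during follow-up. The error always makes change look larger, and it arises only in participants who supply older films.

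There is a lesser consequence for the method comparison. Film-only lesions too recent for the old film are missing from the comparator's baseline count, which slightly favours the scanner.

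**Working it through.** The plan gives no figure for the film-to-film interval, so there is none to reproduce. The check is interval arithmetic.

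**Inputs from the protocol**
- Maximum age of a reused film: 6 months (sections 3 and 8).
- Visual examination and scan: baseline appointment (section 3).
- Follow-up: 1 year, with bitewings repeated only at the final examination (section 3).
- Participants: 70 to be included, 64 required before drop-out (section 5).

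**Assumptions**
- New films are taken at the final examination. The text does not say whether the 6-month allowance also applies there.
- The caries score in section 4 is the combined visual and radiographic one registered in section 3.
- New film-only lesions form at a constant rate.
- The share q of participants reusing films is 25%, 50% or 75%, with a mean film age of 3 months. Section 3 describes radiographs as part of an annual check-up. If check-ups were spread evenly over the year, about half of participants would hold a film under 6 months old, averaging 3 months, which is the middle case.

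**Step 1: range of the gap.** Film to scan: 0 to 6 months. Film to film at a nominal 12-month visit: 12 + 0 = 12 to 12 + 6 = 18 months. The longest interval is 18/12 = 1.5 times the nominal year.

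**Step 2: share of newly seen film-only lesions that predate baseline.** For one participant with film age a, the share is a/(12 + a). At a = 6 it is 6/18 = 33%. Across all participants it is 3q/(12 + 3q):

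| Reuse share q | Mean film-to-film interval (months) | Share predating baseline |
|---|---|---|
| 25% | 12 + 0.75 = 12.75 | 0.75/12.75 = 6% |
| 50% | 12 + 1.5 = 13.5 | 1.5/13.5 = 11% |
| 75% | 12 + 2.25 = 14.25 | 2.25/14.25 = 16% |

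These shares apply to lesions seen only on film. A lesion also visible on examination is registered on the baseline day.

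**Step 3: dependence on visit timing.** Eighteen months is the maximum only if the final visit falls at 12 months. Table 1 puts baseline in January to September 2019 and the final examination in April to September 2020. A participant examined on 1 January 2019 could not have a final examination before about 15 months, so with a 6-month-old film the interval would be at least about 15 + 6 = 21 months.

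**Step 4: size of a same-visit-film subset.** Of 70 participants, 70 × (1 − q) = 52.5, 35 or 17.5 would have baseline-visit films, about 52, 35 or 18, against the 64 calculated.

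**The case against.** The strongest reply is that the comparator as a whole is not out of date. Its visual half is done at the baseline appointment, after cleaning and just before the scan. A new or deepened lesion on a surface the scanner can see is open to that examination. The surfaces that depend most on film are approximal, and section 2 (Background) says the scanner cannot examine them. The same section says radiographs are insensitive to early enamel demineralization, so even a fresh film would miss many of the lesions the study targets. All of this stands.

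It rules out three stronger readings:
- **That an apparent scanner lead at baseline is largely a time gap.** The same-day visual examination covers the surfaces on which the scanner could lead. What remains is a slightly lower comparator total, because section 4 counts lesions per patient without restricting surfaces.
- **That one third of new radiographic lesions predate baseline.** That figure needs a film exactly 6 months old. Across participants, the assumed scenarios give 6% to 16%.
- **That lesions treated since the film remain in the comparator count.** The condition of fillings is registered at the baseline examination, so a restoration placed after the film should be seen.

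It is also fair to say that section 4 plans no separate analysis of radiographic change and calls part of its analysis exploratory. That limits the weight of the point but does not remove it. The unequal interval enters through the combined caries score, and there the scanner's inability to see approximal surfaces gives no protection.

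**Conclusion.** The point holds for the radiographic component of the baseline caries score, in participants who supply existing bitewings. Their film-to-film interval is up to 18 months at a nominal 12-month visit, and film-only lesions formed before baseline can be counted as 1-year change. Under the stated assumptions this affects about 6%, 11% or 16% of newly seen film-only lesions at 25%, 50% or 75% reuse. The share of the total caries change is smaller to the extent that visually detected lesions contribute, and cannot be computed from the protocol.

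The effect on the baseline method comparison is in the scanner's favour, but small and unquantified. The sample size is unaffected. This is a modest bias in a known direction that is cheap to correct in the plan; it does not undermine the study.

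**What to change.** Leave the rule on accepting recent films as it is, so that no participant has additional exposure. Then:

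1. Record the date of every bitewing and report the distribution of film-to-scan and film-to-film intervals. Film age must already be established to apply the 6-month rule.
2. Score bitewing findings so that they can be separated from visual findings. Without this, the radiographic part cannot be put on its own time scale, because the visual part runs from visit to visit.
3. In section 4, express the radiographic part of caries change per film-to-film year.
4. Keep all participants in the main method comparison, with the same combined comparator for everyone.
5. Add a sensitivity analysis of both paired t-tests restricted to participants whose bitewings were taken at the baseline visit.

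Two alternatives should be avoided. Using visual findings alone as the comparator for participants with older films would give different participants different comparators, and it would remove film-only lesions from the comparator count, which itself favours the scanner. Making the same-visit subset the main analysis could leave as few as about 18 participants.

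The cost is separate recording of bitewing findings, a date field and revised wording in section 4. The sensitivity set will be smaller and its estimates less precise.
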